A follow-on Phase 2 study in DNP with 456 patients tested 3 doses of NLX-112 [0.5, 1.0, and 1.5 mg BID (1.0, 2.0, 3.0 mg/day)] vs placebo (Study CP201). Safety and tolerability in this study, which employed an 11-day up-titration period prior to and a 10-day down titration period after the 6-week fixed-dose period, were similar to the previous phase 2 study. Four SAEs occurred but none were related to NLX-112. Dizziness, headache, nausea and insomnia were the most common TEAEs and occurred predominantly during the up-titration period or the first fixed-dose week (Table 6.1-1). Please refer to the NLX-112 Investigators' Brochure for additional details on safety, tolerability and adverse events (AEs) in the NLX-112 phase 2 clinical program.

**Table 6.1-1 Most Common Drug-related TEAEs (incidence > 2% of patients) Listed By Number of Patients in Each Dose Group in Study CP201**

Preferred Term	PBO (N=112)	NLX-112 Groups		
		1 mg (N=113)	2 mg (N=114)	3 mg (N=117)
Dizziness	1 (0.9%)	8 (7.1%)	15 (13.2%)	15 (12.9%)
Nausea	4 (3.6%)	6 (5.3%)	12 (10.5%)	16 (13.7%)
Headache	3 (2.7%)	3 (2.7%)	6 (5.3%)	9 (7.7%)
Insomnia	-	3 (2.7%)	3 (2.6%)	6 (5.1%)

Preferred Term	PBO (N=112)	NLX-112 Groups		
		1 mg (N=113)	2 mg (N=114)	3 mg (N=117)
Withdrawal syndrome	1 (0.9%)	4 (3.5%)	4 (3.5%)	5 (4.3%)
Paresthesia	1 (0.9%)	3 (2.7%)	4 (3.5%)	2 (1.7%)
Vomiting	-	-	-	5 (4.3%)
Hypotension	-	3 (2.7%)	2 (1.8%)	2 (1.7%)
Accidental overdose	1 (0.9%)	3 (2.7%)	3 (2.6%)	2 (1.7%)
Hypertension	-	1 (0.9%)	1 (0.9%)	3 (2.6%)
Mood Swings	2 (1.8%)	-	2 (1.8%)	3 (2.6%)
ALAT increased	1 (0.9%)	1 (0.9%)	3 (2.6%)	-

Thus, based on Phase 1 and 2 study results, NLX-112 could be safely administered up to the dose of 3.0 mg/day with a progressive up-titration to maximize the tolerability of the drug and a down-titration to prevent withdrawal symptoms.

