**Down-titration period (2 weeks, down-titration by 0.25 mg/day every 2 days):**

- Days 43-44 (start of down-titration period [1.75 mg/day])
- Days 45-46 (1.5 mg/day)
- Days 47-48 (1.25 mg/day)
- Days 49-50 (1 mg/day)
- Days 51-52 (0.75 mg/day)
- Days 53-54 (0.5 mg/day)
- Days 55-56 (0.25 mg/day)

Patients in the placebo arm will follow the same dose escalation, constant dose and down-titration schedule, but will be taking the matching placebo tablets. Patients who have intolerable AEs during the 28-day up-titration period will be allowed to return to the previous tolerated dose at the discretion of the Investigator, or they may withdraw from the study if they so choose.

Each patient is expected to participate in the study for approximately 10 weeks, not including screening. Patients will be treated with IMP for a total of 8 weeks (56 days).

The timing of events is summarized in Table 8.1-1. Study assessments are described in Section 11.

Table 8.1-1 Schedule of events

Study visit number		Visit 1	Visit 2	Visit 3	Visit 4	Visit 5	Visit 6	Visit 7	Visit 8	Visit 9
Study period		Screening	Baseline	Phone Safety Visit	Clinic Safety Visit	Clinic Safety Visit	Clinic Efficacy Visit	Clinic Efficacy Visits	Phone Safety Visit	Follow-up Clinic Visit 
Study day	Protocol Section	Day -28 to Day -5	Day 1	Day 7 ±1 day	Day 14 ±2 days	Day 21 ±2 days	Day 28 ±2 days	Day 42 ±2 days	Day 49 ±2 days	Day 70 ±7 days
Informed Consent	14.3	X								
Eligibility criteria	9.4 & 9.5	X	X 							
Demographics	11.1.3	X								
Vital signs 	11.2.3	X	X		X	X	X	X		X
Physical examination	11.2.2	X								X
Body weight and height 	11.1.4	X								X
Hoehn and Yahr scale 	11.1.8	X	X							
Medical and psychiatric history	11.1.5	X								
Pregnancy test 	11.1.7	X	X							X
12-lead ECG	11.2.4	X	X		X	X	X	X		X
Safety laboratory 	11.2.6	X	X		X	X	X	X		X
MMSE	11.1.9	X								
C-SSRS 	11.2.5	X	X		X	X	X	X		X
UPDRS 	11.3.1	X	X				X	X		X
Diary and wearable device training	11.3.3&11.3.6	X	X							
Randomization	9.9		X							
Study drug dispensing	10.5		X				X	X		
Treatment (Day 1 - Day 56)	10.6					X				

Study visit number		Visit 1	Visit 2	Visit 3	Visit 4	Visit 5	Visit 6	Visit 7	Visit 8	Visit 9
Study period		Screening	Baseline	Phone Safety Visit	Clinic Safety Visit	Clinic Safety Visit	Clinic Efficacy Visit	Clinic Efficacy Visits	Phone Safety Visit	Follow-up Clinic Visit 

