Study day	Protocol Section	Day -28 to Day -5	Day 1	Day 7 ±1 day	Day 14 ±2 days	Day 21 ±2 days	Day 28 ±2 days	Day 42 ±2 days	Day 49 ±2 days	Day 70 ±7 days
Diary data collection 	11.3.3		X				X	X		
Wearable device data collection 	11.3.6		X				X	X		
L-DOPA challenge	11.3.1		X				X	X		
UDysRS	11.3.2		X				X	X		
Video taping (UDysRS)	11.3.2		X				X	X		
CGI-S/CGI-C 	11.3.5		X				X	X		
KPPS	11.4.1		X				X	X		
PDQ39	11.4.2		X				X	X		
HADS	11.4.3		X				X	X		
ICIQ-OAB	11.4.4		X				X	X		
ESS	11.4.5		X				X	X		
NLX-112 plasma concentration sampling	11.4.6				X	X	X	X		X
Drug accountability	10.5						X	X		X
Baseline symptoms	11.1.10	X								
Adverse events 	11.2.1						X			
Prior and concomitant medications	11.1.6						X			

CGI-S/CGI-C=Clinical Global Impression of Severity and Clinical Global Impression of Change, C-SSRS=Columbia Suicide Severity Rating Scale, ESS=the Epworth Sleepiness Scale, HADS=the Hospital Anxiety Depression Scale, ICIQ-OAB=the International Consultation on Incontinence Questionnaire Overactive Bladder Module,

KPPS=the King's Parkinson's disease Pain Scale, UPDRS=the Unified Parkinson's Disease Rating Scale, MMSE=Mini Mental Status Exam, PDQ39=the Parkinson's disease Quality of Life Scale (39-item), UDysRS=the Unified Dyskinesia Rating Scale

1. Also early withdrawal follow-up visit
2. Confirmation of eligibility
3. Blood pressure (including orthostatic hypotension assessment), pulse, respiratory rate and temperature. At screening and baseline (Visit 1 and Visit 2), vital signs to assess orthostatic hypotension will be conducted in triplicate, 15-20 minutes apart, with the average of the 3 assessments used for exclusion.
4. Body weight at Visit 1 and Visit 9. Height at Visit 1 only.
5. The Modified Hoehn and Yahr scale will be used to establish the PD stage of the patient.
6. Women of child-bearing potential only.
7. Hematology, coagulation, serum biochemistry and urinalysis.
8. C-SSRS: the baseline scale will be used at the first assessment (screening, Visit 1) and the follow-up scale will be used at all subsequent visits.
9. UPDRS - Screening: part IV only. Other visits: parts I-IV
10. PD Home Dyskinesia Diary: 2 consecutive 24-hour diaries taken prior to the visits indicated above.
11. Wearable data collection will take place during a 2-day period prior to the visits indicated above.
12. CGI-S at baseline (Day 1, Visit 2), CGI-C at other visits.

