#### *11.2.1.6 Time period and frequency for collecting adverse events*

All AEs (including SAEs) will be collected from the start of IMP administration until the end-of-study visit.

Any AE with start date on the day of IMP administration will, if possible, be recorded with start time.

At the end-of-study visit, information on new AEs or SAEs, if any, and stop dates for ongoing events must be recorded as applicable.

Investigators are not obligated to actively seek AEs or SAEs after conclusion of the study participation. However, if the Investigator learns of any SAE, including a death, at any time after a participant has been discharged from the study, and he/she considers the event to be reasonably related to the study intervention or study participation, the Investigator must promptly notify the Sponsor.

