### 7.2 Database modeling of study design

The study design is mapped to a SDTM study design model containing the following structural components:

**EPOCH:** An interval of time in the planned conduct of a study. An epoch is associated with a purpose (e.g., screening, randomization, treatment, follow-up), and applies across all arms of the study. Study epochs follow a controlled terminology to represent the different study parts (e.g. SCREENING, TREATMENT, FOLLOW-UP)

[figure not shown]
**ELEMENT:** Building blocks used to build up the entire study length for all subjects. Information on ELEMENTs is extracted from the study design and schedule of events in the protocol. ELEMENTs are defined to span the entire study without gaps. One EPOCH may contain one or several ELEMENTs. All ELEMENTs must have transition rules in accordance with the protocol to determine start and end.

**ARM:** Subjects are allocated to study arms depending on the study design, either by randomization or other allocation processes defined in the study protocol. ARMs are defined as the total number of planned ways a subject can go through the study (unique combination of study ELEMENTs). All ARMs must contain a unique sequence of ELEMENTs.

**VISIT:** Study visits are defined as planned timepoints during the study where study data is collected. A visit can be performed in clinic, by off-site contact with study personnel (phone call, video conference or similar), or by subject initiated recordings of data. The visit schedule is extracted from protocol and eCRF design.

A schematic representation of the SDTM study design is presented in Figure 1.

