### 9.1 Analysis of the primary endpoints

#### 9.1.1 *Adverse events*

An overview of all AEs, including SAEs, intensity, relationship to IMP, and deaths will be presented by treatment. Incidence of AEs will be summarized by SOC and PT by treatment. Separate tables will be provided, if relevant, for serious AEs (SAEs) or events leading to withdrawal from study. Separate tables will be provided with summaries per titration period as well (up-titration, stable dosing and down-titration).

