**Table AE 3 Overview of adverse events per titration period (Full analysis set)**

Use the same template as for Table AE 1, but include columns (NLX-112 and Placebo respectively) for the up-titration period (up to Visit 6), the stable dosing period (Visit 6 to Visit 7), the down-titration period (from Visit 7) and the Total column -> 7 results columns in all.

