**Table AE 4 Adverse events by system organ class and preferred term per titration period (Full analysis set)**

Use the same template as for Table AE 2, but include columns (NLX-112 and Placebo respectively) for the up-titration period (up to Visit 6), the stable dosing period (Visit 6 to Visit 7), the down-titration period (from Visit 7) and the Total column -> 7 results columns in all.

10.2.2.2 *Physical examination*

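### SAP Tables AE 3 and AE 4 give the down-titration period no end, so adverse events that start after the last tablet are reported as down-titration events

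*SAP*

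**What the plan says.** SAP 9.1.1 adds adverse-event summaries for three phases: up-titration, stable dosing and down-titration. The shells for Tables AE 3 and AE 4 (SAP 10.2.2.1) fix the cuts by visit. Up-titration runs to Visit 6 and stable dosing from Visit 6 to Visit 7. The third phase is "the down-titration period (from Visit 7) and the Total column", and each table is stated to have 7 result columns.

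Protocol 8.1 puts the constant dose on Days 29 to 42 and the taper on Days 43 to 56, for 56 days of treatment in all. Table 8.1-1 places Visit 7 at Day 42 ±2 and the final visit, Visit 9, at Day 70 ±7. Its first footnote on Visit 9 reads "Also early withdrawal follow-up visit". Protocol 11.2.1.6 sets the collection window: "All AEs (including SAEs) will be collected from the start of IMP administration until the end-of-study visit".

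Protocol 6.1.3 gives the reason for the taper, calling for "a down-titration to prevent withdrawal symptoms". Protocol 6.3.1 lists withdrawal symptoms after abrupt stopping at 3.0 mg/day or more among the known risks.

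**The concern.** The first two phases have an end and the third does not. Read as written, the third column takes in every adverse event from Visit 7 to the end of the study, including those that start after dosing is over, and labels them all as down-titration events. If the column were instead cut silently at Day 56, later events would have no phase column at all. Neither reading gives a correctly labelled table.

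Safety and tolerability are the primary objective, and AE 3 and AE 4 are the only planned adverse-event tables by dose phase. In Study CP201, which used a 10-day down-titration, drug-related withdrawal syndrome was reported in 4 of 114 patients at 2 mg/day against 1 of 112 on placebo (Protocol Table 6.1-1). Later studies of this drug will need to know whether such events begin while the dose is coming down or once it has stopped. A pooled column cannot show that.

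**Working it through.** **Reproducing the plan's own figures**
- Treatment days (Protocol 8.1): up-titration 7 steps × 4 days = 28; constant dose Days 29–42 = 14; taper 7 steps × 2 days = 14. Sum: 28 + 14 + 14 = 56, as stated.
- Result columns (SAP Tables AE 3 and AE 4): 3 phases × 2 arms + 1 Total = 7, as stated. No column is left for follow-up.

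**Share of the last column that follows the last tablet**

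Share = (Visit 9 day − last-dose day) / (Visit 9 day − Visit 7 day), with the day of Visit 7 counted in the stable phase.

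- Nominal: (70 − 56) / (70 − 42) = 14/28 = 50%.

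The documents do not settle whether the taper follows the calendar (last dose on Day 56) or starts from the patient's own Visit 7 (last dose 14 days later), so both are shown. Visit 7 varies over Days 40–44 and Visit 9 over Days 63–77.

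| Dosing rule | Lowest share | Highest share |
|---|---|---|
| Calendar, last dose Day 56 | (63 − 56)/(63 − 40) = 7/23 = 30% | (77 − 56)/(77 − 44) = 21/33 = 64% |
| From Visit 7, last dose 14 days later | (63 − 58)/(63 − 44) = 5/19 = 26% | (77 − 54)/(77 − 40) = 23/37 = 62% |

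The overall range is about 26% to 64%. No combination of dosing rule and visit timing brings it to zero.

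**Patients held below 2 mg/day.** The protocol gives no taper schedule for them. Assuming the same 0.25 mg steps every 2 days down from the held dose, with nominal visits, a patient at 1.5 mg/day takes the last tablet on Day 52, a share of 18/28 = 64%. A patient at 1.0 mg/day takes it on Day 48, a share of 22/28 = 79%.

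**How much of that time is drug-free.** With a half-life of 34 to 41 h (Protocol 6.1.3), and taking five half-lives as the end of elimination:
- 5 × 34/24 = 7.1 days; 5 × 41/24 = 8.5 days.
- Of the 14 nominal days after the last tablet, 14 − 8.5 = 5.5 to 14 − 7.1 = 6.9 days are essentially drug-free. That is 20% to 25% of the 28-day column.

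**Expected withdrawal events.** At the CP201 rate for 2 mg/day, 16 × 4/114 = 0.56 in the active arm. The chance of at least one is 1 − (110/114)^16 = 44%.

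**The case against.** The strongest reply is that this is a layout gap in two supplementary tables. AE 1 and AE 2 do not use the cut. Adverse-event start dates are recorded (Protocol 11.2.1.12) and every event is listed (SAP Listing 16.2.7-1), so with 24 patients the split can be rebuilt by hand. Both arms share the same cuts, so the label favours neither. Vital signs, ECG and laboratory data are tabulated by visit and already separate Visit 9 from the dosing visits. Drug persists for a week or more after the last tablet, so discontinuation effects can straddle that date. Assessing the taper is not a stated objective. All of this stands and limits the consequence. It does not make the label correct, and a split rebuilt after unblinding would be post hoc.

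Some stronger readings are tempting but unsupported:
- **That the column overstates taper incidence by a calculable amount.** This would need an event rate after the last dose. The documents give none, and Protocol 6.1.3 places the common events mainly in up-titration or early fixed dosing.
- **That early stoppers have no column.** They can be placed in the phase in which they left, although events after stopping would then carry a dosing label.
- **That the SAP contradicts its own database model.** The follow-up epoch in SAP 7.2 is a generic example, and the design figure is not available.
- **That the visit windows also misplace events at the other phase boundaries.** This depends on calendar dosing, which the documents do not establish.

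**Conclusion.** The point holds as a labelling fault in the phase tables for a primary endpoint. Following the SAP as written, events that start after the last tablet are printed as down-titration events. The affected time is half the column on the nominal schedule and about 26% to 64% across the visit windows for patients completing the 14-day taper. It is larger for patients on reduced doses if their taper is shorter.

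This rests on events being assigned by start date and on the column running to Visit 9, as its wording implies. The figures are shares of calendar time. How many events are affected cannot be known in advance, and few withdrawal events are expected. A reader might infer that post-treatment events will be lost, or that the safety comparison between arms is compromised. Neither follows, because the events remain in AE 1, AE 2 and the listings, and the cuts are the same in both arms. What the plan loses is a prespecified tabulation of whether withdrawal-type events start during the taper or after it. The change is worth making because it is cheap.

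**What to change.** Amend the SAP only, before database lock and unblinding:

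1. In SAP 9.1.1 and Tables AE 3 and AE 4, end the down-titration period on the day of each patient's last recorded IMP dose.
2. Add a post-treatment period, running from after that day to the end-of-study visit, as one extra column pair. Each table then has 4 phases × 2 arms + 1 Total = 9 result columns.
3. Where IMP is stopped permanently before the taper is complete, assign adverse events that start after the stop to the post-treatment period.
4. If the last-dose date is missing, estimate it from that patient's own Visit 7 date and taper schedule. A fixed Day 56 would impose calendar dosing and would be wrong for a shorter taper.

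**Cost.** One SAP paragraph, two more columns per table and slightly sparser cells. A patient with events both during and after the taper is counted in both columns, so patient counts cannot be added across them. No new assessment or protocol change is proposed: adverse-event start dates are captured and an IMP administration listing is planned (SAP Listing 16.2.5-3). Some cleaning of dose dates is likely, because SAP 5.4 draws dosing details partly from eCRF comments and monitoring reports and names only the up-titration and stable periods.

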**Table AE 4 Adverse events by system organ class and preferred term per titration period (Full analysis set)**

Use the same template as for Table AE 2, but include columns (NLX-112 and Placebo respectively) for the up-titration period (up to Visit 6), the stable dosing period (Visit 6 to Visit 7), the down-titration period (from Visit 7) and the Total column -> 7 results columns in all.

10.2.2.2 *Physical examination*
**Table PE 1 Physical examinations (Full analysis set)**

Assessment	Assessment timepoint		NLX-112 (N=XX)	Placebo (N=XX)	Total (N=XX)
[PARAMETER 1]	[Assessment timepoint 1]	[RESULT 1]	x (xx%)	x (xx%)	x (xx%)
		[RESULT 2]	x (xx%)	x (xx%)	x (xx%)
		[RESULT 3]	x (xx%)	x (xx%)	x (xx%)
	[Assessment timepoint 2]	[RESULT 1]	x (xx%)	x (xx%)	x (xx%)
		[RESULT 2]	x (xx%)	x (xx%)	x (xx%)
		[RESULT 3]	x (xx%)	x (xx%)	x (xx%)

Data based on the Full analysis set. SAS program: [PROGRAM NAME].sas. Run by: [USERNAME] YYYY-MM-DDTHH:MM:SS. Data extracted at: YYYY-MM-DDTHH:MM:SS

 10.2.2.3 *Vital signs*
**Table VS 1 Vital signs measurements (Full analysis set)**

Assessment (unit)	Result category	Assessment timepoint		NLX-112 (N=XX)	Placebo (N=XX)	Total (N=XX)
[PARAMETER 1]	Measured value (unit)	[Assessment timepoint 1]	n	xx	xx	xx
			Mean (SD)	x.xx (x.xx)	x.xx (x.xx)	x.xx (x.xx)
			Median (Min, Max)	x.xx (x.x, x.x)	x.xx (x.x, x.x)	x.xx (x.x, x.x)
		[Assessment timepoint 2]	n	xx	xx	xx
			Mean (SD)	x.xx (x.xx)	x.xx (x.xx)	x.xx (x.xx)
			Median (Min, Max)	x.xx (x.x, x.x)	x.xx (x.x, x.x)	x.xx (x.x, x.x)
	Absolute change from baseline	[Assessment timepoint 2]	n	xx	xx	xx
			Mean (SD)	x.xx (x.xx)	x.xx (x.xx)	x.xx (x.xx)
			Median (Min, Max)	x.xx (x.x, x.x)	x.xx (x.x, x.x)	x.xx (x.x, x.x)
	Relative change from baseline (%)	[Assessment timepoint 2]	n	xx	xx	xx
			Mean (SD)	x.xx (x.xx)	x.xx (x.xx)	x.xx (x.xx)
			Median (Min, Max)	x.xx (x.x, x.x)	x.xx (x.x, x.x)	x.xx (x.x, x.x)

Data based on the Full analysis set. n: Number of observations. SD: Standard deviation. NC: Not calculated - number of evaluable observations less than 3. NA: Not available - no evaluable observations. SAS program: [PROGRAM NAME].sas. Run by: [USERNAME] YYYY-MM-DDTHH:MM:SS. Data extracted at: YYYY-MM-DDTHH:MM:SS

## 10.2.2.4 12-lead ECG

**Table EG 1 ECG measurements (Full analysis set)**

Assessment (unit)	Result category	Assessment timepoint		NLX-112 (N=XX)	Placebo (N=XX)	Total (N=XX)	
[PARAMETER 1]	Measured value (unit)	[Assessment timepoint 1]	n	xx	xx	xx	
			Mean (SD)	x.xx (x.xx)	x.xx (x.xx)	x.xx (x.xx)	
		[Assessment timepoint 2]	Median (Min, Max)	x.xx (x.x, x.x)	x.xx (x.x, x.x)	x.xx (x.x, x.x)	
	Absolute change from baseline		n	xx	xx	xx	
			Mean (SD)	x.xx (x.xx)	x.xx (x.xx)	x.xx (x.xx)	
			Median (Min, Max)	x.xx (x.x, x.x)	x.xx (x.x, x.x)	x.xx (x.x, x.x)	
Relative change from baseline (%)	[Assessment timepoint 2]	n	xx	xx	xx	xx	
		Mean (SD)	x.xx (x.xx)	x.xx (x.xx)	x.xx (x.xx)	x.xx (x.xx)	
		Median (Min, Max)	x.xx (x.x, x.x)	x.xx (x.x, x.x)	x.xx (x.x, x.x)	x.xx (x.x, x.x)	

Data based on the Full analysis set. n: Number of observations. SD: Standard deviation. NC: Not calculated - number of evaluable observations less than 3. NA: Not available - no evaluable observations. SAS program: [PROGRAM NAME].sas. Run by: [USERNAME] YYYY-MM-DDTHH:MM:SS. Data extracted at: YYYY-MM-DDTHH:MM:SS

**Table EG 2 ECG interpretations (Full analysis set)**

Assessment	Assessment timepoint		NLX-112 (N=XX)	Placebo (N=XX)	Total (N=XX)
[PARAMETER 1]	[Assessment timepoint 1]	[RESULT 1]	x (xx%)	x (xx%)	x (xx%)
		[RESULT 2]	x (xx%)	x (xx%)	x (xx%)
		[RESULT 3]	x (xx%)	x (xx%)	x (xx%)
	[Assessment timepoint 2]	[RESULT 1]	x (xx%)	x (xx%)	x (xx%)
		[RESULT 2]	x (xx%)	x (xx%)	x (xx%)
		[RESULT 3]	x (xx%)	x (xx%)	x (xx%)

Data based on the Full analysis set. SAS program: [PROGRAM NAME].sas. Run by: [USERNAME] YYYY-MM-DDTHH:MM:SS. Data extracted at: YYYY-MM-DDTHH:MM:SS

## 10.2.2.5 Columbia Suicide Severity Rating Scale (C-SSRS)

**Table CS 1 Columbia Suicide Severity Rating Scale (C-SSRS) changes over time (Full analysis set)**

Use the same template as outlined in Section 0 above.

## 10.2.2.6 Safety laboratory analyses

**Table LB 1 Safety laboratory measurements - clinical chemistry (Full analysis set)**

Assessment (unit)	Result category	Assessment timepoint		NLX-112 (N=XX)	Placebo (N=XX)	Total (N=XX)	
[PARAMETER 1] (unit)	Measured value	[Assessment timepoint 1]	n	xx	xx	xx	
			Mean (SD)	x.xx (x.xx)	x.xx (x.xx)	x.xx (x.xx)	
		[Assessment timepoint 2]	Median (Min, Max)	x.xx (x.x, x.x)	x.xx (x.x, x.x)	x.xx (x.x, x.x)	
	Absolute change from baseline		n	xx	xx	xx	
			Mean (SD)	x.xx (x.xx)	x.xx (x.xx)	x.xx (x.xx)	
			Median (Min, Max)	x.xx (x.x, x.x)	x.xx (x.x, x.x)	x.xx (x.x, x.x)	
Relative change from baseline (%)	[Assessment timepoint 2]	n	xx	xx	xx	xx	
		Mean (SD)	x.xx (x.xx)	x.xx (x.xx)	x.xx (x.xx)	x.xx (x.xx)	
		Median (Min, Max)	x.xx (x.x, x.x)	x.xx (x.x, x.x)	x.xx (x.x, x.x)	x.xx (x.x, x.x)	

Data based on the Full analysis set. n: Number of observations. SD: Standard deviation. NC: Not calculated - number of evaluable observations less than 3. NA: Not available - no evaluable observations. SAS program: [PROGRAM NAME].sas. Run by: [USERNAME] YYYY-MM-DDTHH:MM:SS. Data extracted at: YYYY-MM-DDTHH:MM:SS

**Table LB 2 Safety laboratory measurements - haematology (Full analysis set)**

Use the same format as for Table LB 1.

